Bioanalytical Analysis	Covance Inc. [name]
Radioanalytical Laboratory, Metabolite Profiling and Identification	Covance Laboratories Ltd. [name]
Statistician	

12 December 2018 Page 6 of 72

SYNOPSIS

CONFIDENTIAL

Protocol Reference: BGB-290-106

Title of study: A Phase 1 Study to Investigate the Absorption, Metabolism, and Excretion of [¹⁴C]-Pamiparib following Single Oral Dose Administration in Patients with Advanced and/or Metastatic Solid Tumors

Objectives:

The primary objectives of the study are:

- To assess the disposition of [14 C]-pamiparib following oral administration of a single 60 mg (\sim 100 μ Ci) dose in patients with advanced and/or metastatic solid tumors
- To assess the plasma pharmacokinetics (PK) of total radioactivity and pamiparib following a single oral dose of [14C]-pamiparib
- To determine the whole blood and plasma concentrations of total radioactivity
- To determine the urinary and fecal recovery of total radioactivity

The secondary objectives of this study are:

- To characterize and identify metabolites of [14C]-pamiparib in plasma, urine, and feces
- To determine plasma and urine concentrations of pamiparib and/or its major metabolites
- To assess the safety and tolerability of pamiparib during the treatment phase

Study design:

This is an open-label study, in patients with advanced and/or metastatic solid tumors, which consists of 2 parts: a research phase (inpatient) and a treatment phase.

Part 1 - Research Phase

The research phase of the study will assess the disposition of [14C]-pamiparib following oral administration of a single dose of 60 mg. Patients will be resident at the Clinical Research Unit (CRU) from Day -1 until completion of all assessments on Day 7 but may be discharged earlier at the Principal Investigator's (PI's) discretion if they meet the following discharge criteria:

- Approximately 90% of the radioactive dose is recovered or
- < 1% of the radioactive dose is recovered in urine and feces for 2 consecutive 24-hour collection intervals.

If the discharge criteria have not been met on Day 7, patients may be asked to collect 24-hour excreta samples for up to 7 days on a non-residential basis. Patients may remain resident at the CRU if deemed necessary by the PI for safety reasons. A Follow-up visit will occur within 7 days of discharge from the CRU (if discharged on Day 7 or before), or within 7 days of the patients' final non-residential visit (if additional non-residential visits are required). At the Follow-up visit, patients' ability to continue into the treatment phase will be determined by the PI.

Part 2 - Treatment Phase

The treatment phase of the study will allow patients to have continued access to pamiparib. Safety assessments will be conducted ≤ 7 days prior to the start of pamiparib treatment at either the Follow-up visit for Part 1 or at a separate visit. Patients will undergo 28-day cycles of pamiparib 60 mg twice daily dosing. Pamiparib treatment will be continued unless any of the following occur: progressive disease (PD), unacceptable toxicity, pregnancy, death, withdrawal of consent, lost to follow-up, major protocol violation which in the opinion of the Sponsor would have significant impact on the study or its outcome, start of new anticancer therapy, withdrawal by the PI, or study termination by Sponsor. There will be a Follow-up visit approximately 30 days following the final administration of pamiparib.

12 December 2018 Page 7 of 72

Protocol Amendment Version 3.0 Covance Study: 8381180

Number of patients:

Approximately 10 patients will be enrolled so that 4 patients complete Part 1 of the study.

Diagnosis and main criteria for inclusion:

Patients will be male or female, ≥ 18 years of age, who have histologically or cytologically confirmed malignancy that has progressed to the advanced or metastatic stage. Patients must have an Eastern Cooperative Oncology Group (ECOG) performance status of ≤ 1 .

CONFIDENTIAL

Protocol Reference: BGB-290-106

Investigational products, dose, and mode of administration:

Part 1: A single oral dose of [14 C]-pamiparib 60 mg containing approximately 100 μ Ci (3.7 MBq). Part 2: Oral doses of pamiparib 60 mg twice daily.

Duration of patient participation in the study:

Planned Screening duration: approximately 27 days.

Planned study duration: Part 1 – up to 22 days (Day -1 to Day 21); Part 2 - variable based on time required for study drug discontinuation to occur (see previous section).

Endpoints:

Pharmacokinetics:

Part 1

Plasma, urine, and feces will be collected for the analysis of pamiparib concentrations and total radioactivity. The PK parameters of pamiparib and total radioactivity will be calculated using standard noncompartmental methods. The following PK parameter endpoints for pamiparib in plasma and total radioactivity in whole blood and plasma will be calculated whenever possible: area under the concentration-time curve (AUC) from time zero to infinity (AUC $_{0-\infty}$), AUC from time zero to the last quantifiable concentration (AUC $_{0-t}$), maximum observed concentration (C $_{max}$), time of C $_{max}$ (t $_{max}$), and apparent terminal elimination half-life (t $_{1/2}$). The apparent total clearance (CL/F) and apparent volume of distribution (V $_z$ /F) will also be determined.

The $AUC_{0-\infty}$ of plasma pamiparib relative to $AUC_{0-\infty}$ of plasma total radioactivity ($AUC_{0-\infty}$ Plasma pamiparib/Total Radioactivity Ratio) and $AUC_{0-\infty}$ of whole blood total radioactivity to $AUC_{0-\infty}$ of plasma total radioactivity ($AUC_{0-\infty}$ Blood/Plasma Ratio) will be calculated.

The following PK parameter endpoints for pamiparib and total radioactivity in urine will be calculated whenever possible: amount excreted in urine (A_{eu}) , cumulative A_{eu} , percentage excreted in urine (f_{eu}) , and cumulative f_{eu} . The renal clearance (CL_R) will also be determined for pamiparib. The following PK parameter endpoints for total radioactivity in feces will be calculated whenever possible: amount excreted in feces (A_{ef}) , cumulative A_{ef} , percentage excreted in feces (f_{ef}) , and cumulative f_{ef} .

Plasma, urine, and fecal samples will also be used to establish the metabolic profile of pamiparib and to identify its metabolites.

Part 2

No analysis of pamiparib PK will be conducted during the treatment phase.

Safety

Safety endpoints for this study include AEs, vital sign measurements, 12-lead electrocardiograms, clinical laboratory evaluations, and physical examinations. Tumor assessments will be conducted using a computerized tomography or magnetic resonance imaging scan at Screening and every 12 weeks following the baseline scan. The ECOG performance status will be assessed during Part 1 and Part 2.

Statistical methods:

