7. STUDY ASSESSMENTS AND PROCEDURES

Every effort will be made to schedule and perform the procedures as closely as possible to the nominal time, giving consideration to appropriate posture conditions, practical restrictions, and the other procedures to be performed at the same timepoint.

In Part 1, the recommended order of priority for scheduling procedures around a timepoint is (in descending order of priority):

- Physical examinations
- ECOG
- Vital sign measurements
- ECGs
- Blood and urine samples for clinical laboratory evaluations
- Dosing
- Blood samples for PK assessments of pamiparib, total radioactivity, and metabolites
- Start and end of urine and fecal collections for PK assessments.

In Part 2, assessments will be conducted at study visits as in the Schedule of Assessments in Appendix 4.

Pharmacokinetic Assessments (Part 1 Only) 7.1.

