Patients must be supine for at least 5 minutes before blood pressure, heart rate, and temperature measurements. During the in-house period in Part 1, blood pressure, heart rate, and temperature measurements should be conducted in the morning.

7.2.4. 12-Lead Electrocardiogram

Resting 12-lead ECGs will be recorded after the patient has been supine and at rest for at least 5 minutes at the times indicated in the Schedule of Assessments in Appendix 4.

Single 12-lead ECGs will be repeated once if outside the clinical reference range.

12 December 2018 Page 41 of 72 In the case of an abnormality such as prolonged QT interval corrected for heart rate using Fridericia's formula > 500 msec or > 60 msec from the highest baseline or predose value, new arrhythmia, or other clinically significant finding, ECGs will be recorded in triplicate at least 2 minutes apart.

CONFIDENTIAL

Additional 12-lead ECGs may be performed at other times if judged to be clinically appropriate or if the ongoing review of the data suggests that a more detailed assessment of ECGs is required. The PI (or designee) will perform a clinical assessment of each 12-lead ECG.

7.2.5. **Physical Examination**

Complete and limited physical examinations will be performed at the timepoints specified in the Schedule of Assessments in Appendix 4. A complete physical examination includes a review of the following systems: head/neck/thyroid; eyes/ears/nose/throat; respiratory; cardiovascular; lymph nodes; abdomen; skin; musculoskeletal; and neurological. A limited physical examination includes an assessment of the patient's general appearance, skin, thorax/lungs, cardiovascular, and abdomen.

7.2.6. **Eastern Cooperative Oncology Group**

The ECOG performance status will be evaluated at the times indicated in the Schedule of Assessments in Appendix 4.

7.2.7. **Tumor Assessments**

Tumor imaging (CT or magnetic resonance imaging [MRI], with preference for CT) will be performed at Screening or Part 2 Pre-dose Visit and every 12 weeks (± 7 days) from the time of the Part 2 C1D1. At the PI's discretion, CT or MRI scans may be repeated at any time if PD is suspected.

A CT scan or MRI of the thorax, abdomen, and pelvis plus other relevant evaluations as appropriate will be performed to assess all known disease.

The same imaging technique should be used for each patient throughout the study.

7.3. **End-of-Treatment Visit**

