9. SAMPLE SIZE AND DATA ANALYSIS

9.1. **Determination of Sample Size**

No formal statistical assessment of sample size has been conducted. The sample size chosen for this study is common in human radiolabeled studies and is considered sufficient to achieve the objectives of the study. Up to approximately 10 patients will be enrolled and studied in order that 4 patients complete Part 1 of the study.

12 December 2018 Page 53 of 72

9.2. **Analysis Populations**

9.2.1. **Pharmacokinetic Population**

The PK population will include all patients who received [14C]-pamiparib and have evaluable PK data. Patients will be excluded from the PK summary statistics and statistical analysis if a patient has an AE of vomiting that occurs at or before 2 times median t_{max} .

CONFIDENTIAL

9.2.2. **Safety Population**

The safety population will include all patients who received [14C]-pamiparib.

9.3. **Pharmacokinetic Analyses**

Plasma and urine PK parameters of pamiparib and whole blood and plasma parameters of total radioactivity will be calculated using standard noncompartmental methods.

Additional noncompartmental PK parameters may be determined where appropriate.

Pharmacokinetic parameters will be summarized using descriptive methodology. No formal statistical analysis will be performed.

Descriptive statistics (mean, median, minimum, maximum, standard deviation, geometric mean, and geometric coefficient of variation) will be calculated for all PK parameters and PK concentration data where applicable.

Specification of PK parameters to be presented in the CSR; procedures for accounting for missing, unused, or spurious data; procedures for reporting deviations from the original statistical plan; and selection of patients to be included in the analyses population(s) will be presented in the CSR and/or the Statistical Analysis Plan as appropriate.

All statistical summary calculations will be performed using SAS® Version 9.4 or greater.

9.4. **Safety Analysis**

All AEs will be listed and summarized using descriptive methodology. No formal statistical analysis will be performed. The incidence of AEs will be presented by severity and by relationship with the study drug as determined by the PI (or designee). Each AE will be coded using the Medical Dictionary for Regulatory Activities.

Patient ECOG performance will be reported for the Safety population and will be listed.

9.5. **Interim Analysis**

No interim analyses are planned for this study.

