Appendix 4: Schedule of Assessment

Schedule of Assessments - Part 1

			Days			
Study Procedures	Screening ^a	-1	1	2-7	7-14 ^b	Part 1 Follow- up Visit ^c
Informed consent	X					
Inclusion/exclusion criteria	X	X				
Demographic data ^d	X					
Medical history/current medical conditions ^e	X					
Alcohol breath test	X	X				7
Serology	X					
Follicle-stimulating hormone ^f	X					
Pregnancy test ^g	X	X				
Height	X					
Body weight	X	X				X
ECOG performance status	X	X	X			
Tumor assessments: CT or	X					
MRI scan	Λ					
Study residency:						
Check-in		X				
Check-out				X^b		
Non-residential visit	X				X	X
Study drug administration:						
[¹⁴ C]-pamiparib (60 mg)			X			
Pharmacokineticsh:						
Blood sampling for pamiparib concentration (plasma) ^{h 1}			X	X	X	
Blood sampling for total radioactivity (whole blood and plasma) ^{h 2}			X	X	X	

12 December 2018 Page 62 of 72

Complete physical

Limited physical examination¹

examination^k

			D/1 E W			
Study Procedures	Screening ^a	-1	1	2-7	7-14 ^b	Part 1 Follow- up Visit ^c
Blood sampling for metabolite profiling and identification (plasma) h 3			X	X		
Urine collection for pamiparib concentration, total radioactivity, and metabolite profiling and identification ^{h 4}			X	X	X	
Fecal collection for total radioactivity and metabolite profiling and identification ^{h 5}			X	X	X	
Safety and tolerability:						
Adverse event recording	X	X	X	X	X	X
Prior/concomitant medication monitoring	X	X	X	X	X	X
Clinical chemistry, hematology, and urinalysis	X	X		X (Day 5)		X
Vital signs ⁱ	X	X	X	X (Day 5)	X	X
12-lead electrocardiogram ^j	X	X	X	X (Day 5)		X

CONFIDENTIAL

X

Protocol Reference: BGB-290-106

Abbreviations: CT = computed tomography; ECG = electrocardiogram; ECOG = Eastern Cooperative Oncology Group; MRI = magnetic resonance imaging; QTc(F) = QT interval corrected for heart rate using Fridericia's formula.

a. Screening: Screening period extends from Day -28 to Day -2. The Screening assessments must be performed within 28 days before dosing.

X

X

b. **Discharge:** Patients can be discharged on Day 7, or before at the discretion of the PI if the discharge criteria are met: approximately 90% mass balance recovery, or < 1% of total dose recovered in urine and feces for 2 consecutive 24-hour collection intervals. If the discharge criteria have not been met on Day 7, patients may be asked to collect 24-hour excreta samples for up to 7 days on a non-residential basis.

X

X (Day 5)

X

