10.5.6 Eastern Cooperative Oncology Group (ECOG) Performance Status

The frequency of patients with each grade will be presented for ECOG performance status data by part and listed for individual patients.

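### Part 1 schedules no ECOG performance status after Day 1, so the Part 1 ECOG table very likely holds no post-dose value

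*Protocol*

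**What the plan says.** The protocol treats ECOG performance status as one of the safety and tolerability assessments for both parts (Section 7.2). The synopsis says "The ECOG performance status will be assessed during Part 1 and Part 2". Section 7.2.6 gives no times of its own: "The ECOG performance status will be evaluated at the times indicated in the Schedule of Assessments in Appendix 4". In that appendix, the Part 1 row carries three marks, under Screening, Day -1 and Day 1. The cells for Days 2-7, Days 7-14 and the Part 1 Follow-up visit are empty. The Part 2 schedule has ECOG on Day 1 of each cycle and at the End-of-treatment visit, but not at the predose visit or the safety follow-up.

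On reporting, Protocol 9.4 says "Patient ECOG performance will be reported for the Safety population and will be listed"; Section 9.2.2 defines that population as everyone given [14C]-pamiparib. SAP 10.5.6 says "The frequency of patients with each grade will be presented for ECOG performance status data by part", with individual listings as well. SAP Section 9 defines a separate Safety Population for each part.

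**The concern.** A safety table for a dosing period is normally read as showing how patients were after the dose. Here the Part 1 ECOG table would very likely show only how they were before it. Entry requires ECOG 0 or 1 at Screening (inclusion criterion 4), and eligibility is checked again on Day -1, so the table's content is largely settled by the entry criteria.

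The patients most affected are those who are dosed and then do not enter Part 2. The next ECOG on either schedule is Cycle 1 Day 1, which they never reach. Whether they should have an ECOG at their last visit depends on how footnote c is read, and sites could read it differently.

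**Working it through.** No power or sample-size arithmetic applies. The check sets the schedule rows and their footnotes side by side.

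1. **Are the columns read correctly?** The Body weight row just above the ECOG row shows Screening, Day -1 and Follow-up, with the cells between empty. The columns have therefore not shifted in extraction, and the empty ECOG cells after Day 1 are genuine.

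2. **Is the Day 1 value predose?** Section 7 introduces its list with "In Part 1, the recommended order of priority for scheduling procedures around a timepoint is (in descending order of priority". ECOG is second in that list and dosing is sixth. The order is a recommendation, and the schedule does not label the Day 1 ECOG as predose, so predose is most likely but not certain. A value taken later on Day 1 would still be a same-day value.

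3. **Count.** Scheduled Part 1 ECOG assessments: 3. Scheduled after Day 1: 0. The synopsis gives Part 1 as up to 22 days, Day -1 to Day 21. Days 2 to 21 are 21 - 2 + 1 = 20 days, so up to 20 of the 22 days have no scheduled ECOG.

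4. **Comparison with other safety measures in Part 1.** Clinical laboratory tests, vital signs and ECG are marked on Day 5 and at Follow-up. Body weight is marked at Follow-up. Adverse events are recorded throughout. Among these, ECOG alone has no mark after Day 1.

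5. **Footnote c.** It is attached to the Part 1 Follow-up column. For a patient discontinued from the study, it says that this visit counts as the End-of-treatment visit. Protocol 7.3 takes the required End-of-treatment assessments from Appendix 4, and the only End-of-treatment column there, in the Part 2 schedule, includes ECOG. The column that carries the footnote does not. On one reading ECOG is due at that visit. On the other, the visit merely replaces a separate End-of-treatment visit and no ECOG is due.

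6. **Effect of moving one mark.** Screening, Day -1 and Follow-up: still 3 assessments, with 1 after Day 1 instead of 0. SAP 10.1.1 defines baseline as the last value before dosing in that part, so Day -1 becomes the Part 1 baseline with no change to the definition.

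**The case against.** The plan does not contradict itself on the main point. The synopsis promises ECOG in Part 1, and it is done in Part 1. Neither Protocol 9.4 nor SAP 10.5.6 promises a post-dose Part 1 value or a change from baseline. ECOG is not among the secondary endpoints in Protocol 2.2.2, and the safety objective concerns the treatment phase, where ECOG is scheduled regularly. Part 1 is a single-dose disposition study that needs 4 completers; an uncontrolled ECOG value on a variable Follow-up day says little about the drug. All of this stands and keeps the point small.

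Three stronger readings are tempting, and the documents do not support them.

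- *Decline after dosing goes unrecorded.* Only the ECOG grade is missing. Adverse events, which include worsening of existing conditions and the symptoms of progression, are collected until 30 days after the last dose or the start of new anticancer therapy. Laboratory tests, vital signs, ECG and weight are taken at Follow-up.
- *The ECOG results are biased toward no decline.* No planned output estimates ECOG change across the two parts. Each part has its own Safety Population and its own table. Any figure for such a bias would follow from assuming that the patients who decline are exactly those not entered in Part 2, and no entry rule in the documents says that.
- *Entry to Part 2 is decided without performance status.* The synopsis leaves the decision to the investigator at Follow-up, and ECOG is scheduled at Cycle 1 Day 1 before the first Part 2 dose. There is no contradiction to report.

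**Conclusion.** The point holds as a minor gap in the schedule with one mismatch to reconcile. That no ECOG is marked after Day 1 in the Part 1 columns is certain from Appendix 4. That the Part 1 table holds no post-dose value at all is very likely; it rests on the recommended order in Section 7 being followed on Day 1. That a dosed patient who does not enter Part 2 has no clearly scheduled later grade depends on footnote c, which can be read either way and, on its wording, covers only patients discontinued from the study. No primary or listed secondary endpoint is affected.

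**What to change.** In the Part 1 schedule of Appendix 4, move the Day 1 ECOG mark to the Part 1 Follow-up visit and keep Day -1 as the baseline under SAP 10.1.1. In SAP 10.5.6, tabulate Part 1 ECOG as baseline against Follow-up for the Part 1 Safety Population. Every dosed patient who attends Follow-up then has a post-dose grade, and the Follow-up column agrees with footnote c on ECOG.

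The cost is one mark moved and one line in the SAP. The number of ECOG assessments per patient stays at 3, and the visit already takes place. What is lost is a repeat baseline value about a day after the first. If the sponsor wants to keep the Day 1 value, adding a mark at Follow-up closes the gap equally well, with 4 assessments instead of 3.

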Append	dix 8: Contraception Guidelines and Definitions of "Women of Childbearing Potential", "No Childbearing Potential"
	LIST OF FIGURES
Figure	1: Pamiparib Activity with Etoposide and Carboplatin and as Maintenance Monotherapy in BCLU-053 Small Cell Lung Cancer Xenograft Model19
Figure	2: Pamiparib Activity with Etoposide and Carboplatin and as Maintenance Monotherapy in BCLU-080 Small Cell Lung Cancer Xenograft Model20
Figure	3: Study Schematic: Part 1
Figure	4: Study Schematic: Part 2
	LIST OF TABLES
Table 1	: PARP Enzyme Inhibition and PARP Trapping Activity of PARP Inhibitors
Table 2	2: Dose Levels for Pamiparib
Table 3	2: Criteria for Modification of Pamiparib Dosing for Related Adverse Events
Table 4	

12 December 2018 Page 12 of 72

LIST OF ABBREVIATIONS

CONFIDENTIAL

Protocol Reference: BGB-290-106

Abbreviation	Definition
AE	adverse event
A_{ef}	amount excreted in feces
A_{eu}	amount excreted in urine
ALT	alanine aminotransferase
AML	acute myeloid leukemia
ANC	absolute neutrophil count
AST	aspartate aminotransferase
AUC	area under the concentration-time curve
$\mathrm{AUC}_{0\text{-}\infty}$	area under the concentration-time curve from time zero to infinity
AUC _{0-∞} Blood/ Plasma Ratio	area under the concentration-time curve from time zero to infinity of whole blood total radioactivity to area under the concentration-time curve from time zero to infinity of plasma total radioactivity
AUC _{0-∞} Plasma pamiparib /Total Radioactivity Ratio	area under the concentration-time curve from time zero to infinity of plasma pamiparib relative to area under the concentration-time curve from time zero to infinity of plasma total radioactivity
$\mathrm{AUC}_{0 ext{-t}}$	area under the concentration-time curve from time zero to the last quantifiable concentration
BID	twice daily
BRCA	breast cancer susceptibility gene
¹⁴ C	carbon-14
CFR	Code of Federal Regulations
СНО	Chinese hamster ovary
CKD-EPI	Chronic Kidney Disease Epidemiology Collaboration
CL/F	apparent total clearance
CL_R	renal clearance
C_{max}	maximum observed concentration
CNS	central nervous system
CR	complete response
CRO	Contract Research Organization
CRU	Clinical Research Unit
CSR	Clinical Study Report
CT	computed tomography
CYP	cytochrome P450
DLT	dose-limiting toxicity
ECOG	Eastern Cooperative Oncology Group

12 December 2018 Page 13 of 72

CONFIDENTIAL Protocol Reference: BGB-290-106

EDC electronic data capture E/C etoposide and carboplatin

EC Ethics Committee

EC₅₀ half-maximal effective concentration

ECG electrocardiogram

eCRF electronic Case Report Form

EOT end-of-treatment

FDG-PET fluorodeoxyglucose-positron emission tomography

 f_{ef} percentage excreted in feces f_{eu} percentage excreted in urine FSH follicle-stimulating hormone

GCP Good Clinical Practice
GFR glomerular filtration rate

hERG human ether-à-go-go related gene

IB Investigator's Brochure

IC₅₀ half-maximal inhibition concentration

ICF Informed Consent Form

ICH International Council for/Conference on Harmonisation ICRP International Commission on Radiological Protection

IMP investigational medicinal productMDRD Modification of Diet in Renal Disease

MDS myelodysplastic syndrome
MRI magnetic resonance imaging
MTD maximum tolerated dose

PAR poly (ADP-ribose)

PARP poly (ADP-ribose) polymerase

PD progressive disease
PI principal investigator
PK pharmacokinetic(s)
PR partial response

QWBA quantitative whole-body autoradiography

QTc(F) QT interval corrected for heart rate using Fridericia's formula

SAE serious adverse event SCLC small cell lung cancer

SD stable disease

SEM standard error of the mean SOP standard operating procedure

12 December 2018 Page 14 of 72

SSBs single-strand DNA breaks

SUSAR suspected unexpected serious adverse reaction

 $t_{1/2}$ apparent terminal elimination half-life TEAE treatment-emergent adverse event

t_{max} time of maximum observed concentration

ULN upper limit of normal

V_Z/F apparent volume of distribution

12 December 2018 Page 15 of 72

